structive pulmonary disease, obstructive sleep apnoea, restrictive lung disease, pulmonary hypertension), kidney disease (chronic with/without dialysis), liver disease other than cancer (HBV/HCV/HDV chronic viral hepatitis, other chronic disease, cirrhosis), metabolic disease, immunosuppressive conditions (solid organ transplant recipient, auto-immune diseases), cancer (solid cancer, haematological malignancies, type of primitive cancer/haematological malignancies, presence of metastases, if ongoing chemotherapy), mental or neurological disorders (psychiatric illness, anxiety disorder, mood disorder, psychotic disorder, Alzheimer disease, dementia other than Alzheimer, Parkinson's disease, myasthenia gravis, epilepsy, stroke (with/without residual deficits, neuromuscular disease, multiple sclerosis), muscular dystrophy, amyotrophic lateral sclerosis); TB co-infection; other opportunistic co-infection (specify) for HIV population

- 5. Comorbidity management: drug name and dose (to include only treatments taken regularly)
- 6. Anti-COVID therapy: drug name, maintenance dose, and duration
- 7. Antibiotic therapy: drug name, dose, duration, and type of treated infection
- Oxygen therapy: nasal prongs, face mask, face mask with reservoir, high-flow nasal cannula, noninvasive ventilation, mechanical ventilation; numbers of O₂ (L/min) provided (maximum reached) and fraction of inspired O₂ (FiO₂) provided (maximum reached)
- 9. SARS-CoV-2 vaccination: vaccine name, date of administration
- Relevant new medical events or worsening of previous conditions, including deep venous thrombosis, pulmonary embolism, infections (including a new SARS-CoV-2-infection during follow-up), malignancies (type of cancer, overall stage).
- 11. Symptoms: abdominal pain, ageusia/dysgeusia, anosmia, balance impairment, behaviour disorder, chest pain or chest tightness, confusion, cough, delirium, diarrhoea, disrupted sleep, dizziness, dysp-noea, fatigue, fever (including low-grade fever), headache, hypothermia, impaired cognitive status, lethargy, loss of appetite, mood affective disorder, myalgia, nausea/vomiting, palpitation, phlegm, runny nose, sore throat, stuffed nose, syncope, wheeze.
- 12. WHO Clinical Progression Scale
- 13. Vital signs: dead/alive, blood pressure, body temperature, heart rate, respiratory rate, peripheral oxygen saturation

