5. BACKGROUND

The ongoing COVID-19 pandemic has created a global public health emergency that is challenging societies, health care systems and national economies worldwide [1]. Since the beginning of the pandemic, our knowledge of transmission dynamics [2], clinical presentation [3], long-term sequelae [4], and risk factors for disease progression [5-7] has been increasing steadily. Evidences on the efficacy of treatment strategies coming from clinical trials [8] have been obtained and preventive measures such as social distancing and vaccination campaigns, have been put in place. Nonetheless, there is still an urgent need for a more standardized research activity, connecting multiple countries and settings and focusing on the different aspects of this pandemic. High-quality data and biological samples collection coming from large multicentric cohorts are urgently required and have not yet been implemented in an international level. Evidence-based knowledge is required to enable rapid and effective decision-making, with particular attention to the transferability of the collected information.

COVID-19 can result in prolonged illness, even in young adults and children without underlying chronic medical conditions. In a telephone survey conducted by the Centers for Disease Control and Prevention among a random sample of 292 adults (≥18 years) who had a positive outpatient test result for SARS-CoV-2 by RT-PCR, 35% of 274 symptomatic respondents reported not having returned to their usual state of health 2 weeks or more after testing [9]. The burden of COVID-19 long-term sequelae and the exact underlying pathophysiology mechanisms remain unknown. Results from the follow-up of large cohorts are particularly needed to fully understand the characteristics and risk factors for SARS-CoV-2 infection long-term consequences.

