11. RECRUITMENT STRATEGY

Inpatients will be recruited by the study team at the treating hospital. Outpatients will be recruited by the study team in the emergency rooms, outpatient clinics, and through the coordination with regional primary care networks, who will offer the opportunity to enter the study to patients with active or previous COVID-19. This allows a broad recruitment of cases and the rapid inclusion of additional study centers in regional hotspots.

Patients will be followed up for up to 18 months after the SARS-CoV-2 infection diagnosis. The recruitment can take place at any time between the SARS-CoV-2 infection diagnosis and the end of the 18month follow-up, provided that the patient ensures at least one follow-up visit. Discharged inpatients as well as recovered outpatients will be invited to participate by a phone call (which will be repeated once in case of no reply). The screening/baseline data collection (including the informed consent process) can be carried out on the same day of a follow-up visit.

Before the first patient is recruited at a location, the responsible investigator ensures that all legal and regulatory requirements are met. Patients can revoke their consent to participate in the study without restriction at any time and at their own request, without giving reasons and without any consequences for their future treatment. In case of loss to follow-up, the previous follow-up assessments will be included in the data analyses. Patients will be recruited until January 2023 and followed-up until June 2023, allowing a partial follow-up for participants whose SARS-COV-2 infection occurred after January 2022.

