13. STATISTICAL ANALYSIS

Sample size calculation. The number of inclusions will depend on the progress of the SARS-CoV-2 pandemic, which is unknown at this time. Therefore, the number of patients who will be included cannot be determined in advance. However, depending on the timing of the project and the included cohorts, the expected enrollment is 10000 subjects.

We will carry out comprehensive descriptive analyses taking into account sociodemographic factors and clinical courses. The frequency distributions of the characteristics will be given in absolute and relative numbers, median plus interquartile range (IQR) or mean values plus 95% confidence interval (CIs). Associations with specific treatment strategies, disease severity patterns and laboratory results will be analysed using chi-square tests, t-tests or Mann-Whitney tests, depending on the data. To evaluate potential risk factors, multivariate regression models will be carried out. Outcome time analyses using Cox proportional-hazards regression models with time-dependent covariates will be performed to examine

factors associated with each endpoint (including death). In addition, we will use cumulative incidence functions, such as the Fine-Gray subdistribution hazard regression model, to account for competing events (i.e., relocation, discharge against medical advice, etc.). For missing values, a different strategy to understand the causes and the significance for the analysis will be developed and a graduated procedure for dealing with censorship and imputations via linked regressions will be developed. The significance level is defined with a p-value <0.05. All statistical analyses will be carried out with STATA, Python and/or R statistics software by trained staff (epidemiologists, statisticians) using the latest analysis methods.

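### The Fine-Gray analysis names relocation and discharge against medical advice as competing events, although neither prevents sequelae, re-infection or death

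*Combined protocol and SAP*

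**What the plan says.** Section 13 (Statistical analysis) plans Cox models with time-dependent covariates to study "factors associated with each endpoint (including death"). It then continues: "In addition, we will use cumulative incidence functions, such as the Fine-Gray subdistribution hazard regression model", with the stated purpose "to account for competing events (i.e., relocation, discharge against medical advice, etc".). Relocation and discharge against advice are the only competing events named. Death appears only as an endpoint.

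The endpoints have to be read from section 8 (Objectives): the type, rate and length of sequelae, and the rate and determinants of re-infection. Section 7 sets the horizon at up to 18 months after diagnosis, in hospitalised and non-hospitalised patients.

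Nothing elsewhere recodes the two exits as censoring. Section 11 keeps the assessments made before a patient is lost, but gives the loss no status in the time-to-event models. Section 13 defers the rest: a "graduated procedure for dealing with censorship and imputations via linked regressions will be developed".

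**The concern.** A competing event removes the possibility of the endpoint. Relocation does not; it may only end observation. Discharge against advice need not even do that. Leaving hospital does not put a patient out of the study's reach, since section 11 recruits after discharge as well: "Discharged inpatients as well as recovered outpatients will be invited to participate by a phone call".

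The Fine-Gray model keeps people with a competing event in the risk set as people who can no longer have the endpoint. For someone who has moved away, that is a strong and false assumption of zero later risk. Two consequences follow.

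- The cumulative incidence becomes the chance of being seen to have the event before moving or leaving. The objectives ask for the chance of having it.
- If exits differ by country, care setting or severity, part of that difference shows up as a risk-factor effect. Differences are plausible: the cohorts span many countries and both care settings, and section 12 leaves the organisation of visits to each centre.

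Meanwhile the event that does preclude later sequelae and re-infection is not named as competing. Death is captured at each visit (section 3.2, footnote 13: "Vital signs: dead/alive, blood pressure, body temperature").

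**Working it through.** The plan states no event rate, exit rate or power, so there is no figure to reproduce. The size can only be illustrated.

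**Inputs from the documents**
- Horizon: 18 months (section 7).
- Expected enrolment: 10,000 (section 13).
- Illustrative risk: 35%, the only figure for prolonged illness in the documents (section 5: "35% of 274 symptomatic respondents reported not having returned to their usual state of health 2 weeks or more after testing"). It is a two-week outpatient figure, used here only as a stand-in for an 18-month risk R. A second value, R = 10%, is assumed.

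**Assumptions**
- The proportion d leaving by relocation or discharge against advice over 18 months is 2% to 40%. Other loss to follow-up is not counted.
- Hazards are constant, and exit is independent of the event.

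**Cumulative incidence.** With λ = −ln(1 − R)/18 and μ = −ln(1 − d)/18, coding exits as competing gives

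CIF(t) = λ/(λ + μ) × [1 − exp(−(λ + μ)t)].

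Censoring them gives 1 − exp(−18λ) = R at 18 months.

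Example with R = 35%, d = 20%: λ = 0.02393, μ = 0.01240, and exp(−18(λ + μ)) = 0.65 × 0.80 = 0.52. So CIF = 0.6588 × 0.48 = 31.6%.

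| Exits by 18 months | 2% | 5% | 10% | 20% | 30% | 40% |
|---|---|---|---|---|---|---|
| True risk 35% | 34.7% | 34.2% | 33.3% | 31.6% | 29.8% | 27.9% |
| True risk 10% | 9.9% | 9.7% | 9.5% | 9.0% | 8.4% | 7.9% |

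**Shorter follow-up.** Section 11 provides for late infections by "allowing a partial follow-up for participants whose SARS-COV-2 infection occurred after January 2022". With the same hazards and a 6-month window, the true 13.4% becomes 13.3%, 13.1% and 12.9% at 18-month exit proportions of 5%, 10% and 20%. The bias is small there.

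**Against sampling error.** At 35% and 10,000 subjects the 95% half-width is 1.96 × √(0.35 × 0.65/10,000) = 0.93 points. The bias equals this at d = 5.7%. At R = 10% the half-width is 0.59 points and the crossing is at d = 11.7%.

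**Subdistribution hazard ratio.** This is the large-sample root of the partial-likelihood score for two equal groups, with exited people kept at risk to month 18 and reference risk 35%.

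| True HR | Exits, reference v comparison | Subdistribution HR |
|---|---|---|
| 1.00 | equal | 1.00 |
| 1.00 | 2% v 5% | 0.98 |
| 1.00 | 5% v 10% | 0.97 |
| 1.00 | 5% v 15% | 0.94 |
| 1.00 | 10% v 30% | 0.88 |
| 1.00 | 30% v 10% | 1.14 |
| 1.50 | 20% v 20% | 1.49 |
| 1.50 | 5% v 30% | 1.27 |

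**Simulation check.** With 10,000 subjects, 1,000 replicates, a true HR of 1.00 and exits of 5% v 15%, the subdistribution test at two-sided 0.05 rejects in 38% of replicates. With exits censored it rejects in about 5%, and the mean HR is 1.00.

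**The case against.** **Endpoints are undefined.** Section 13 names only death, without setting or horizon. The study also collects length of stay and ICU admission, and one cohort consists of hospitalised patients. For an in-hospital endpoint, discharge against advice could properly compete. This is fair, and the fix leaves room for it. But the plan defines no such endpoint, and the argument does not rescue relocation.

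**The list is open-ended.** It may be meant to include death. That would not make the two named events correct.

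**The phone call in section 11 is a recruitment step, not a retention route.** This stands. For patients enrolled after discharge, the discharge precedes entry and is not an exit at all, so fewer people are affected. It also means the label cannot be right for those patients.

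**The sizes are soft.** This stands too. Exits of 20% to 40% are high for these two causes alone, and constant hazards are a simplification. Exits at day 0 make the bias larger: 5% would give 0.95 × 35% = 33.25%, against 34.2%. Early onset of sequelae makes it smaller. The 5.7% crossing needs a 35% risk and all 10,000 followed to month 18; with an assumed 3,000 analysed it is 10.3%.

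**Censoring is not neutral.** Leaving against advice may be related to severity, so censoring is unbiased only if exit is non-informative given the covariates. This is correct and calls for a sensitivity analysis. Treating these people as having no later risk is still the stronger assumption and does not remedy informative exit.

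**Conclusion.** The plan is wrong as written. For 18-month sequelae, re-infection and death, relocation and discharge against advice are not competing events, and no other text turns them into censoring. The direction is certain: cumulative incidence is lowered, and subdistribution hazard ratios are distorted when exits differ by covariate. With equal exits a null effect stays null and a non-null one is only slightly attenuated.

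The size depends on rates that the documents do not give. Under the assumptions above it is under one point at 5% exits and a 35% risk, 3.4 points at 20%, and smaller for lower risks or short follow-up. The error is confined to the supplementary analysis, provided the Cox models censor at these exits. It should be fixed: cumulative incidence is a natural estimate of the rates that section 8 makes a main objective, and the correction is cheap.

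**What to change.** Replace the bracket in section 13 with wording to this effect:

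> Death is the competing event for non-fatal endpoints (re-infection, onset or resolution of sequelae). Relocation, withdrawal and loss to follow-up are censored at last contact. Patients discharged against medical advice remain in follow-up and are censored only if contact is lost. All-cause death is analysed with no competing event.

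If an in-hospital endpoint is intended, name it and list its competing events separately. Keep the Cox models for determinants and describe them as cause-specific. Because exit may be informative, inverse-probability-of-censoring weights are a reasonable sensitivity analysis.

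The cost is one sentence, a recoded event-status variable and a last-contact date for each participant. No visits or tests are added. The weighting, if used, needs a model for censoring.

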14. REGULATORY, ETHICAL, AND STUDY OVERSIGHT CONSIDERATIONS

14.1 Regulatory and ethical aspects

The study protocol is designed and will be conducted to ensure adherence to the principles and procedures of Good Clinical Practice and to comply with Italian laws, as described in the following documents and accepted, with their signature, by the study investigators: 1. ICH harmonized tripartite guidelines for good clinical practice 1996.2. Directive 91/507 / EEC, The Rules Governing Medicinal Products in the European Community. 3. Legislative Decree No. 211 of 24 June 2003.4. Legislative Decree n.200 November 6, 2007.5. D.M. 21 December 2007.6. AIFA Determination March 20, 2008. All essential clinical documents will be kept to demonstrate the validity of the study and the integrity of the data collected.

All the document and protocol, protocol amendments, ICF, and other relevant documents must be submitted by the principal investigator to the ethical committee of the promotor center and reviewed and approved by the ethical comittae before the study is initiated. The protocol will also be submitted to the local ethics committees of the participating centers by the centers themselves.

14.2 Financial disclosure

Finance and insurance are addressed in the Investigator and/or CRO agreements, as applicable.

14.3 Informed consent process

Participant's informed consent/assent must be obtained and documented in accordance with local regulations, ICH-GCP requirements, and the ethical principles that have their origin in the principles of the

Declaration of Helsinki. Prior to obtaining informed consent, information should be given in a language and at a level of complexity understandable to the participant in both oral and written form by the Investigator (or designee).

Each participant will have the opportunity to discuss the study and its alternatives with the Investigator. Prior to participation in the study, the ICF should be signed and personally dated by the participant, or his/her legal representative.

The participant or his/her legal representative must receive a copy of the signed and dated Informed Consent form. As part of the consent process, each participant must consent to direct access to his/her medical records for study-related monitoring, auditing, IRB/IEC review, and regulatory inspection. If the ICF is amended during the study, the Investigator must follow all applicable regulatory requirements pertaining to the approval of the amended Informed Consent form by the IRB/IEC and use of the amended form.

The participant may withdraw their consent to participate in the study at any time.

14.4 Data protection

The participant must be informed that his/her personal study-related data will be used by the promotor in accordance with local data protection law. The level of disclosure must also be explained to the participant who will be required to give consent for their data to be used as described in the informed consent.

Participants will be assigned a unique identifier by the Promotor. Any participant records or datasets that are transferred to the sponsor will contain the identifier only; participant names or any information which would make the participant identifiable will not be transferred.

The electronic case report form (eCRF) will be provided using RedCap® software of the University Hospital of Verona. Investigators from participating study sites log into the system with username and a safe password including letters, numbers, and symbols.

Investigators will be informed about handling of their personal data and their IP and location during the registration process.

The data collection could be performed also retrospectively after a patient case has been completed (treatment is finished or patient's death). This process will be compliant with all applicable European

and German federal data protection regulations, including EU directive 2016/679 and the German DS-GVO.

14.5 Data collection

Patient data will be collected through a specific eCRF created for the study, which will not contain personal data suitable for identifying the patient. The clinical and outcome information collected in relation to the study will be limited to the objectives of the study, taking care to reduce as much as possible the burden for the patient and for the enrolling clinical center. Only the enrolling clinical center will have access to the patient's identity and will be able to contact him if the coordinating center needs to have further information or for follow-up checks during or after the closure of the study being analyzed and reporting. For each patient, a special unique digital identification code (barcode) will be provided. The code will consist of a three-character part to identify the recruiting center and a second part consisting of 5 digits to identify the enlisted person. The code will be associated with the patient by the clinical center, which will keep a copy of it in the patient file and in the medical record. Each patient enrolled will have a specific study file with all ethical and clinical documentation. The manual for compiling the eCRF will be provided in the Trial Master File.

The data will be entered directly into the patients' eCRF and the related clinical and outcome information will be digitized in a specific database that will be developed using the RedCap® data capturing platform. The system has been successfully used in the network to which the centers are part of SOLIDAR-ITY. RedCap®, installed on protected servers of the Integrated Hospital of Verona, is periodically updated and allows you to create accounts for users, control their access for data entry, limit user privileges (access only to the data of your center) and closure of the validity of the account at the end of the study.

14.6 Data quality assurance

All participant data relating to the study will be recorded on printed, or eCRF unless transmitted to the Sponsor or designee electronically (eg, laboratory data). The Investigator is responsible for verifying that data entries are accurate and correct by physically or electronically signing the eCRF or paper CRF. The Investigator must maintain accurate documentation (source data) that supports the information entered in the eCRF or paper CRF. The Investigator must permit study-related monitoring, audits, IRB/IEC review, and regulatory agency inspections and provide direct access to source data documents.

The Promotor is responsible for the data management of this study including quality checking of the data.

14.7 Source Document

All source documents must be accurate, clear, unambiguous, permanent, and capable of being audited. They should be made using some permanent form of recording (typing, printing, optical disc). They should not be obscured by correction fluid or have temporary attachments (such as removable self-stick notes). Source documents are original records in which raw data are first recorded. These may include hospital/clinic/general practitioner records, charts, diaries, x-rays, laboratory results, pharmacy records, care records, ECG or other printouts, questionnaires, or video, for example. Source documents should be kept in a secure, limited access area.

14.8 Study and site closure

The study start date is the date the clinical study will be open for the recruitment of participants. The first step for recruitment is informed consent and will be the start date of the study.

The study centers will be closed upon completion of the study. A center will be considered closed when all required study documents and materials have been collected and a study closing visit has been performed in the center.

